2. SPECIFIC AIMS

Primary Aim: Test the hypothesis that TRIUMPH intervention participants will have higher rates of biochemically validated, 7-day point-prevalence smoking abstinence at 18 months than TAU participants.

Secondary Aims:

1. Determine the effect of the TRIUMPH intervention compared to TAU on other CVD risk behaviors and factors:
 - a. Continuous smoking abstinence;
 - b. Weight and Body Mass Index;
 - c. Physical fitness with 6-minute walk test;
 - d. Healthy diet by self-report;
 - e. 10-year risk of cardiovascular events with the Global Framingham Risk Score;
2. Determine the effects of the TRIUMPH intervention on patient-reported and other outcomes: health status (SF-12); quality of life (Euroqol); psychiatric symptoms (BPRS); and acute care visits and hospitalizations;
3. Evaluate potential mediators of outcome (e.g., intervention attendance, text-messaging use, quit attempts, pharmacotherapy), and explore outcomes in selected subgroups of interest at baseline (e.g., those willing to set a quit date in 1 month, psychiatric diagnosis).
4. Assess costs per participant and cost-effectiveness incorporating long-term changes in CVD risk.
6. Assess factors that could facilitate implementation, and plan for future implementation and dissemination.

Protocol: Trial of Integrated Smoking Cessation, Exercise and Weight Management in SMI

Improving smoking abstinence, physical activity, diet and weight is critical to decrease premature CVD mortality in SMI, and will require innovative, integrated interventions in community settings. The TRIUMPH Trial will test such an approach that reaches a broad range of smokers with SMI and is practical to implement.

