To assess social networks around smoking, we will use the personal network approach measurement (also called the 'egocentric' approach) to elucidate the network ties that surround a focal individual.¹⁷⁵⁻¹⁷⁹ In particular, we will ask each participant to identify the wide range of network members with whom individuals interact and measure the participant's understanding of the connections among those people. We will assess health literacy with the Health Literacy Skills Instrument. The sexual behaviors of persons with serious mental illness have implications for their emotional and physical well-being. These behaviors also affect the need for health care services that are focused on sexually transmitted diseases, family planning, and childbearing. Reproductive health will be measured with NHANES survey questions.¹⁸⁰ Health care access will be measured using adapted specific Behavioral Risk Factor Surveillance System Questions.¹⁸¹ Access to technology will be measured using adapted questions based on PEW Research Center.¹⁸²

Table 2. Data Collection Measures for All Participants	BL	6	12	15	18
Contact information	X	X	X	X	X
Demographics	X	X			X
Medical conditions	X	X			X
Substance Abuse	X	X	X	X	X
Medical history	X				X
Rose Angina	X				
Psychiatric diagnoses	X				
Medications	X	X	X	X	X
Physical measures					
Blood pressure	X	X			X
Weight	X	X	X	X	X
Height	X				
Waist circumference	X	X			X
6 minute fitness walk	X	X			X
Fasting blood measures	X				X
Urinary Cotinine and anabasine	X	X	X	X	X
Urinary Protein	X				X
Smokerlyzer CO	X	X	X	X	X
Instruments					
Healthy diet	X	X			X
Tobacco measures	X	X	X	X	X
Health status	X	X			X
Quality of Life	X	X			X
Neighborhood Questionnaire	X				X
Sleep habits	X				X
Medication Adherence	X	X	X	X	X
Psychiatric Symptoms	X	X			X
Physical Activity	X	X			X
Social Support					
Healthcare access questions	X				X
Technology	X				X
Reproductive health	X				X
Social Networks	X				X
Health Literacy	X				
Event Surveillance-safety	X	X	X	X	X

Event surveillance. We will identically apply a process to each randomized group and collect self-reported symptoms, health care utilization and records related to CVD and mental health outcomes, including ED use and hospitalizations, and use the SAFTEE¹⁸³ for possible medication side effects.

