13. DATA ANALYSIS

Primary Outcome: The primary outcome will be 7-day point prevalence smoking abstinence at 18 months, defined as self-report of 7 days of not smoking, confirmed by expired CO <8ppm with a Bedfont Smokerlyzer II.^{148,153,218 182} Biochemical verification with available urine cotinine (if not on NRT) and/or anabasine will be used as needed to verify self-reported abstinence, particularly if the validity of CO is expected to be low (e.g. COPD or difficulty forming an adequate seal on the smokerlyzer); and if CO is greater than 8 as this could be from second hand smoke or smoked cannabis.¹⁴⁸⁻¹⁵⁰

7-day smoking abstinence at 6,12 and 15 mo. are secondary outcomes.

Other Secondary outcomes focus on AHA metrics for health risk behaviors²⁰² and include: a) continuous abstinence with 1) % continually abstinent over 3 mo. (based on self-reports of abstinence since last visit, using timeline follow-back²¹⁹, and biochemical verification at 15 and 18 month visits), 2) total days abstinent in the study with the same method, b) Weight and BMI; c) Physical fitness with 6-minute walk;¹⁵⁴⁻¹⁵⁶ and d) Healthy diet.¹⁶⁰ We will assess 10-year probability of a CVD event with the global Framingham Risk Score (FRS) incorporating smoking, total and HDL-cholesterol, systolic blood pressure and diabetes mellitus.²²⁰ Others include: health status (SF-12)¹⁶²; Quality of life (Euroqol);¹⁶³⁻¹⁶⁵ psychiatric symptoms (BPRS);¹⁷⁰ ED use and hospitalizations.

We will also examine the difference of mean CO change over time between intervention arms, and, among continuing cigarette smokers, change of mean number of cigarettes smoked per day over time between intervention arms.

For the primary outcome, we will also perform sensitivity analyses using expired CO<6ppm for abstinent confirmation, as this cutpoint has become more acceptable during the time the trial has been implemented.¹⁵⁰ The outcome using this alternative definition will be modeled in the same fashion.

Our recruitment goal is 220 participants will be recruited from 2 community mental health organizations, enrolled, and randomized in equal allocation to active intervention (Group B) and control (Group A), stratified

Protocol: Trial of Integrated Smoking Cessation, Exercise and Weight Management in SMI

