Although model (1) will support our principal analyses, there is an attractive, transition model alternative. A first-order, autoregressive transition model is a useful adjunct to (1). Note for each participant the outcome is a binary time series that can be analyzed via a series of linked, 2×2 tables (rows are values at visit $(j-1)$, columns at visit j , where visit 0 is baseline), with transitions modeled by logistic regression with treatment effects and, if desired, other covariates. This model could be used to characterize probability of successful abstinence at 12-months among those who were still smokers at 6-months, and at 18-months among those who were smokers at 12-months. Similarly we could estimate relapse rate at a given visit among quitters at the previous visit.

Missing data: Based on our experience, we anticipate less than 10% of follow-up data will be missing.¹²⁵ Prevention is far superior to statistical treatments; every effort will be made to collect data on all randomized. We will use two approaches to missing data. First, in smoking cessation trials, conventionally, those missing smoking data are assumed to be smoking, and we will use this method to be comparable to the field.

^{203,204,222,223} Second, we will perform analyses on the assumption that data is missing at random (MAR). The underlying missing data process determines the biasing effects of missing data and structures valid analytic strategies.²²⁴ If the probability of a potential observation being missing depends on what has, but not on what has not been observed, termed MAR, then estimates based on an appropriate analytic model (both the mean and error structure) for the observed data will not be biased. A valid model for the observed data allows the missing data process to be ignored. If missing is informative, meaning that the probability of an observation being missing depends on the value of that observation after accounting for all the observed data, then bias cannot be avoided by modeling the observed data alone, and the impact should be evaluated using sensitivity analysis. Given that MAR is not a testable hypothesis, we will perform sensitivity analyses to evaluate the robustness of MAR results with multiple imputation using a model derived from our analytical model under MAR, maintaining the covariance structure and modifying the imputation mean according to informative missing data scenarios.

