Secondary Analyses (Secondary Aims 1-2): The odds ratio of maintaining continuous abstinence over 15 to 18 months months will be modeled using logistic regression. To evaluate between group difference in change for secondary continuous outcomes such as continuous smoking abstinence (number of days abstinent), weight, 6-minute walk test, global FRS, and psychiatric symptoms (BPRS), we will use linear mixed models employing visit by intervention interaction terms in the mean model and unstructured correlation in the covariance model to estimate intervention effects over time. Outcomes will be log-transformed as appropriate. Emergency department visits and hospitalizations over the three 6-month periods (0-6, 6-12, 12-18 months) will be modeled using mixed effect Poisson regression. All these analyses will be conducted under intention to treat principles. Covariates such as study site and set quit date indicators and other variables associated with

Protocol: Trial of Integrated Smoking Cessation, Exercise and Weight Management in SMI

presence of missing data will be included in the mean model as appropriate.

We will also explore the difference of mean CO change over time between intervention arms, and, among continuing cigarette smokers, change of mean number of cigarettes smoked per day over time between intervention arms using mixed effects regression modeling approach in a similar fashion. For the first exploratory analysis, we will use all patients in the analysis. In the second analysis, we will determine if patients who continue to smoke, smoke less. In this analysis, we will include only patients who are not abstinent. We will use the pattern mixture approach by examining patients in separate groups according to their pattern of missing data to better understand the probability of missing based on patterns of the observed data to inform proper modeling and sensitivity analyses addressing potential informative missing mechanism.

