Cost Analysis (Aim 4) will be conducted primarily from an adopting organization or payer's perspective (e.g., Medicaid) estimating incremental intervention implementation costs relative to control. Resource measurement will focus on sampling and tracking intervention staff time. We will sample at specified intervals for 1 week at a time. Tracking specific tasks will allow us to eliminate time spent strictly on research and perform sensitivity analyses with different potential levels of efficiency (e.g., amount of active client involvement vs. administrative time). We will use medication data and data on MD visits and hospitalizations to calculate cost per participant and total costs. With estimates of total costs, we will estimate incremental intervention costs and incremental costs per incremental improvement in 1° and 2° outcomes. To extend the time horizon forward, we will use the global FRS to project the proportion expected to have a CV event within 10 years and the present value of costs and QALYs associated with events, allowing us to perform a societal perspective cost-utility analysis.²²⁶ For all analyses, we will conduct univariate sensitivity analyses by varying assumptions and assess estimate uncertainty by bootstrapping for 10000 replications, drawing samples with replacement where samples have the same number of observations as the main study.²²⁷

Qualitative Analysis (Aims 5-6): Interviews will be transcribed and coded. NVivo will be used to enter and group discrete passages from data into themes. We will use the constant comparative method²²⁸ to categorize transcript statements that demonstrate common attributes, then combine categories into broader, recurrent themes using a hybrid approach where we will start with larger categories and then add nodes and subnodes as new concepts emerge until saturation of ideas is reached. Findings will be shared with study sites and the Advisory Committee to inform ongoing implementation and future sustainability and dissemination.

Power analyses: Under a conservative set of assumptions, this trial with sample size of 220 will have ≥80% power to detect a clinically meaningful effect in our primary outcome of 7-day point prevalence smoking abstinence at 18 months between intervention and control (Table 5). We assume:

1. Two-sided alpha =0.05.

2. Follow-up for primary outcome=100%. In smoking cessation trials, those lost to follow-up are classified as

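### The Poisson mixed model for ED visits and hospitalizations leaves its random effects, target contrast and overdispersion handling unstated; in its usual form, period-specific standard errors are too small if events cluster

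*Combined protocol and SAP*

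**What the plan says.** Acute care use is a secondary outcome. Secondary Aim 2 in section 2 lists "psychiatric symptoms (BPRS); and acute care visits and hospitalizations". Section 7 (Event surveillance) says the same process is applied to both arms to collect "health care utilization and records related to CVD and mental health outcomes, including ED use and hospitalizations".

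The count model is given in one sentence of section 13, under Secondary Analyses: "Emergency department visits and hospitalizations over the three 6-month periods (0-6, 6-12, 12-18 months) will be modeled using mixed effect Poisson regression". The surrounding text adds intention to treat and covariates such as site, quit-date readiness and predictors of missingness. For these counts the plan does not state:

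- which random effects are included;
- whether the treatment effect is one overall ratio or one per period;
- whether there is an exposure offset;
- whether ED visits and hospitalizations are modelled separately or pooled;
- how overdispersion is handled, or what kind of standard error is used.

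The neighbouring sentence on continuous outcomes is more explicit: "we will use linear mixed models employing visit by intervention interaction terms in the mean model and unstructured correlation in the covariance model". It does not say that the same contrast applies to the counts.

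**The concern.** The usual Poisson mixed model has one random intercept per person. That intercept absorbs stable differences between people. Given the person, however, each period's count must still have variance equal to its mean. If one exacerbation leads to several ED visits or a readmission in the same 6 months, the counts vary more than that, and nothing in the written plan covers the excess.

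The three-period layout, and the visit-by-arm terms used for the other longitudinal outcomes, make period-specific effects a natural reading of the target. Those are the contrasts that suffer. At stake is a spurious benefit or harm in acute care use in one period, or a spurious shift in the effect over time.

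**Working it through.** **Inputs from the documents.** "Our recruitment goal is 220 participants" with equal allocation gives 220 / 2 = 110 per arm, over three periods. "Two-sided alpha =0.05" is stated for the primary outcome and is carried over here. On missing data, "we anticipate less than 10% of follow-up data will be missing"; the main simulation sets this to zero.

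**Inputs not in the documents.** No event rate, between-person variance or dispersion is given, so all three are assumed and varied. The plan also gives no power or precision figure for this outcome, so there is nothing to reproduce first.

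**Variance.** For a person with rate m per period, the random-intercept Poisson model sets Var(Y | person) = m. Suppose bursts multiply that rate, independently in each period, by a factor with mean 1 and variance κ. Then Var(Y | person) = m + κm² = m(1 + κm). At m = 1 and κ = 0.5, 1, 2 the variance is 1.5, 2 and 3 times the Poisson value. A Poisson standard error for that person's count is then 1/√1.5 = 0.82, 1/√2 = 0.71 and 1/√3 = 0.58 of the true value.

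**Why contrasts differ.** The overall ratio compares people's totals. Bursts make totals more variable, and the fitted intercept variance can grow to match. A period contrast also depends on how each total splits across periods. Given the total, the model fixes the variance of that split and has no parameter to absorb the excess.

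**Main simulation, no treatment effect.** Assumptions: person log-SD 1.0, gamma burst factor, 400 trials per setting, random-intercept Poisson with model-based errors. Simulation error at 5% is √(0.05 × 0.95 / 400) = 1.1 points. Each cell shows median model SE / empirical SD, then the rejection rate at |z| > 1.96.

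| Mean rate per period | κ | Overall 18-month ratio | 12-18 month effect | Change in effect, 0-6 to 12-18 |
|---|---|---|---|---|
| 0.3 | 0 | 1.00, 5.5% | 0.96, 4.8% | 0.95, 5.8% |
| 0.3 | 1 | 0.96, 4.8% | 0.84, 10.0% | 0.76, 14.2% |
| 0.3 | 2 | 0.97, 6.0% | 0.79, 12.8% | 0.65, 21.0% |
| 1.0 | 0 | 1.03, 4.3% | 1.07, 3.7% | 0.98, 5.2% |
| 1.0 | 0.5 | 0.99, 3.5% | 0.86, 8.7% | 0.68, 18.2% |
| 1.0 | 1 | 0.92, 6.2% | 0.80, 12.0% | 0.54, 28.7% |
| 1.0 | 2 | 0.94, 6.5% | 0.72, 17.0% | 0.43, 40.7% |

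The κ = 0 rows are near nominal throughout, so the inflation is not a fitting artefact.

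**A different burst distribution.** Two further simulations used log-normal bursts, 0.5 events per period and person log-SD 1.0. With within-period log-SD s, κ = exp(s²) − 1, so s = 0.5, 0.8, 1.0 gives κ = 0.28, 0.90, 1.72.

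- The 12-18 month effect rejected in 7.5%, 9.8% and 18% in one simulation, and in 7%, 11% and 16% in the other (5.5% without bursts).
- The overall or average effect rejected in 7%, 9% and 9% in one, and in 6-10% in the other.

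**Pooling.** If the two event types are pooled, an ED visit that ends in admission counts twice. Assumptions: 0.3 or 0.6 episodes per period, person log-SD 1.0, 50% or 80% of episodes counted twice, 600 trials per setting. Rejection was 8.7-12.5% for 12-18 months and 11.7-14.8% for the change, against 4.5-6.5% without double counting. The overall ratio rejected in 6.8-9.5%.

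**Remedies, κ = 0.5 to 2 in the main simulation.**

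- Negative-binomial mixed model: 4.8-6.2% (12-18 months) and 4.0-6.5% (change).
- Person-clustered robust errors on the Poisson mixed model: 4.8-6.8% and 5.5-8.3%.
- In the log-normal settings, a Poisson mean model with robust errors gave 5.2-7.6% (4000 trials per setting).

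**The case against.** The strongest reply is that the plan never makes the assumption at issue. A Poisson model with an extra random effect for each person-period is also a mixed-effect Poisson model, can be estimated with three periods per person, and would cover bursts. This stands. A reader might infer that the plan commits to a wrong model, but the text only leaves the model open, and its most common form is the vulnerable one.

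Second, the overall 18-month ratio is close to valid without any change: 3.5-6.5% in the main simulation with bursts, against 3.5-7.0% for the negative-binomial model. The log-normal and pooling runs put it somewhat higher, at 6-10%. This largely stands. It would be wrong to say that every standard error is too small.

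Third, the dispersion is assumed. The documents do not show that these events cluster, and the largest 12-18 month figure needs within-period variation as large as the differences between people. With mild bursts (s = 0.5), 7-7.5% lies within the range of the robust alternative. This stands as a limit on size. It does not remove the gap, because the plan has no check that would detect clustering.

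Fourth, a reader might extend the concern to cost and safety. The Cost Analysis in section 13 assesses uncertainty with 10000 bootstrap replications. Section 17 generally tracks and reports ED use and hospitalization outside its adverse-event definition, although hospitalization for suicidal or homicidal ideation is an adverse event. No safety decision in the documents rests on this model's p-value.

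**Conclusion.** The point holds as a gap in specification with a conditional consequence. If the model is fitted with only a person intercept and model-based errors, and if events cluster within periods, a nominal 5% test rejects a true null in about 7-18% of trials for the 12-18 month effect. For change in effect between periods the figure is 14-41%. The overall 18-month ratio is only slightly affected. These ranges rest on assumed mean rates of 0.3 to 1.0 per period, person log-SD 1.0, and either κ from 0.5 to 2 or within-period log-SD from 0.5 to 1.0.

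The consequence is confined to one secondary outcome. The primary abstinence analysis is untouched. This is a minor point, worth making because it is so cheap to settle before the data are analysed.

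**What to change.** Keep the three periods and the rate ratio, and add to section 13:

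- the target contrast (overall, period-specific, or both), and whether ED visits and hospitalizations are modelled separately;
- the random effects, with observed time in each period as an offset;
- a negative-binomial mixed model, or a person-period random effect in the Poisson model, as the main analysis; alternatively, Poisson regression with person-clustered robust standard errors.

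The negative-binomial model performed best on the period contrasts. Robust errors alone may remain slightly above nominal with 110 per arm. Poisson GEE would match the approach already chosen for the primary outcome. With a log link and a random intercept whose distribution is the same in both arms, its rate ratio equals the person-specific one.

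The cost is a sentence or two in the plan, and slightly wider intervals if the counts prove to be truly Poisson.

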▪ Review by treating psychiatrist required for those inpatient psychiatric hospitalization within six months of enrollment.

▪ Review by treating physician (and anticonvulsant required) for those with seizure disorder with seizure in past six months. Review by treating physician with anticonvulsant or dose adjustment required for those taking medications that lower seizure threshold (e.g., clozapine ≥ 500 mg).

▪ Pregnant, breastfeeding, or planning a pregnancy during study period.

▪ Active substance use disorder, alcohol use disorder, or problem drinking (more than 14 drinks per week for women, more than 21 drinks per week for men)

▪ Planning to leave mental health program or move out of geographic area within 18 months

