7. DATA COLLECTION AND MEASUREMENTS

Outcomes and Measures are collected at baseline, 6, 12, 15 and 18 months at mental health programs. Table 2 shows these measures.

Primary Outcome: The primary outcome will be 7-day point prevalence smoking abstinence at 18 months, defined as self-report of 7 days of not smoking, confirmed by expired CO <8ppm with a Bedfont Smokerlyzer II.^{175,181,182} Biochemical verification with available urine cotinine (if not on NRT) and/or anabasine will be used as needed to confirm self-reported abstinence, particularly if the validity of CO is expected to be low (e.g. COPD or difficulty forming an adequate seal on the smokerlyzer); and if CO is greater than 8 as this could be from second hand smoke or smoked cannabis.¹⁴⁸⁻¹⁵⁰

7-day smoking abstinence at 6, 12 and 15 mo. are secondary outcomes.

Other Secondary outcomes focus on AHA metrics for health risk behaviors¹⁶⁵ and include: a) continuous abstinence with 1) % continually abstinent over 3mo. (based on self-reports of abstinence since last visit, using timeline follow-back)¹⁸³, and biochemical verification at 15 and 18 month visits), 2) total days abstinent in the study with the same method; b) Weight and BMI; c) Physical fitness with 6-minute walk;¹⁸⁴⁻¹⁸⁶ and d) Healthy diet.¹⁸⁷ We will assess 10-year probability of a CVD event with the global Framingham Risk Score (FRS) incorporating smoking, total and HDL-cholesterol, systolic blood pressure and diabetes mellitus.¹⁸⁸ Others include: health status (SF-12)¹⁸⁹; Quality of life (Euroqol);¹⁹⁰⁻¹⁹² psychiatric symptoms (BPRS);¹⁹³ ED use and hospitalizations.

We will also examine the difference of mean CO change over time between intervention arms, and, among

Protocol: Trial of Integrated Smoking Cessation, Exercise and Weight Management in SMI

continuing cigarette smokers, change of mean number of cigarettes smoked per day over time between intervention arms.

Measurement methods: Measures for all participants are detailed below, and will be conducted using standardized procedures, and following quality control procedures as in ACHIEVE and Drs. [name]' trials.^{51,61,121,125} The data collection team will be certified in and experienced with measures, and monitored by the study coordinator. All measures are collected at baseline, 6, and 18 months. At 12 months and 15 months we collect contact information, medications, smoking information, weight and event surveillance.

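### Baseline emergency and hospital use is not pre-specified as a covariate in the Poisson models for ED visits and hospitalizations, although event surveillance is scheduled at baseline

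*Combined protocol and SAP*

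**What the plan says.** Under Secondary Analyses in Section 13: "Emergency department visits and hospitalizations over the three 6-month periods (0-6, 6-12, 12-18 months) will be modeled using mixed effect Poisson regression". The covariate sentence that closes the same paragraph applies to all the secondary models. It reads "Covariates such as study site and set quit date indicators and other variables associated with" and continues, after a page break, "presence of missing data will be included in the mean model as appropriate". Prior use is neither named nor ruled out. In the same paragraph the continuous secondary outcomes are analysed as change, so their baseline values enter. Nothing similar is said of the two count outcomes.

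On data collection, Section 7 opens with "Outcomes and Measures are collected at baseline, 6, 12, 15 and 18 months at mental health programs". In Table 2 the row "Event Surveillance-safety" is marked at baseline, 6, 12, 15 and 18 months. The text below the table says the study will apply one process to both arms and "collect self-reported symptoms, health care utilization and records related to CVD and mental health outcomes, including ED use and hospitalizations". No look-back period is given for the baseline visit.

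The eligibility table in Section 5 adds: "Review by treating psychiatrist required for those inpatient psychiatric hospitalization within six months of enrollment". Section 9 stratifies randomization by site and quit-date readiness only.

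**The concern.** Acute-care counts usually vary widely between people, and a few frequent users can supply much of the total. Someone with a recent psychiatric admission can enrol after review, and nothing in the randomization balances prior use between arms of about 110. A random intercept allows for differences between people, but it does not use information on which people were heavy users before randomization.

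A baseline count of the same event is often the strongest available predictor of later counts. If it was collected and is left out, the interval for the rate ratio may be wider than necessary, and a chance excess of frequent users in one arm stays in the estimate. ED visits and hospitalizations are named under Secondary Aim 2. The open covariate wording would allow prior use to be added later, but that leaves the choice until after the data have been seen.

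**Working it through.** **No figure to reproduce.** Section 13 gives power for the primary outcome and precision for weight, six-minute walk and the global FRS. It gives no rate, dispersion, power or precision for ED visits or hospitalizations. The size of any gain therefore has to be explored under assumptions.

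**Inputs from the documents.** 220 participants in equal allocation, so 220 / 2 = 110 per arm; 18 months of follow-up in three 6-month periods.

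**Assumed inputs, not in the documents.** Mean of 0.25, 0.5 or 1.0 events per 6 months; between-person SD of the log rate of 0.5, 1.0 or 1.5; correlation of a person's log rate between baseline and follow-up of 0.5 or 1.0; no true treatment effect.

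**Method.** Each simulated person has a log-normal rate, a 6-month baseline count and an 18-month follow-up total. The log rate ratio is estimated by a marginal Poisson model with treatment alone, and again with log(1 + baseline count) added, over 600 runs per scenario. The measure is the empirical SE with adjustment divided by the empirical SE without it. For example, at mean 0.5, SD 1.0 and correlation 1.0, the ratio is 0.160 / 0.202 = 0.79.

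| Mean per 6 months | SD of log rate | SE ratio, correlation 0.5 | SE ratio, correlation 1.0 |
|---|---|---|---|
| 0.25 | 0.5 | 1.00 | 1.01 |
| 0.25 | 1.0 | 1.01 | 0.91 |
| 0.25 | 1.5 | 0.97 | 0.71 |
| 0.5 | 0.5 | 0.99 | 1.00 |
| 0.5 | 1.0 | 0.98 | 0.79 |
| 0.5 | 1.5 | 0.95 | 0.53 |
| 1.0 | 0.5 | 0.98 | 0.97 |
| 1.0 | 1.0 | 0.95 | 0.66 |
| 1.0 | 1.5 | 0.96 | 0.42 |

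**Bias.** The mean unadjusted log rate ratio stayed within about 0.02 of zero in every scenario.

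**Second model.** A negative binomial model of the 18-month total is closer to a random-intercept Poisson. With log(baseline count + 0.5) as the covariate and 0.3 to 0.6 events per 6 months, the adjusted-to-unadjusted variance ratios were 0.83 to 0.98 at correlation 0.5, 0.62 to 0.89 at 0.7, and 0.31 to 0.86 at 1.0. As SE ratios, the first range is √0.83 = 0.91 to √0.98 = 0.99.

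**Chance imbalance.** In the second model, among runs where baseline use happened to be more than 1 SD higher in one arm, the unadjusted rate ratio averaged 1.04 to 1.48 with no true effect. After adjustment it averaged 0.95 to 1.07.

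**Limit.** Both models collapse follow-up to one total per person. They stand in for the planned three-period mixed model and do not replicate it.

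**The case against.** The strongest reply is that nothing in the quoted model is wrong. Counts after randomization are the proper outcome, randomization protects the unadjusted contrast, and a valid standard error already reflects chance imbalance. That stands. A reader might infer bias or a mis-set start at month 0; the documents and the simulations support neither.

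Other stronger readings also fail:

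- **That the plan excludes prior use.** The covariate list is open, so the accurate statement is that prior use is not pre-specified.
- **That a six-month baseline count is known to exist.** Table 2 has a safety-surveillance row and no utilization row, and no look-back is stated. The general line "All measures are collected at baseline, 6, and 18 months" does not settle it, because Table 2 itself departs from it (the Rose Angina row is marked at baseline only). The eligibility item concerns psychiatric admissions only and yields neither a count nor ED data.
- **That the gain can be stated as a saving in participants.** A large figure requires person-level use to be very stable and very uneven, and the documents show neither.
- **That the cost analysis is affected.** Section 13 costs medication, physician-visit and hospitalization data directly and bootstraps them; it does not use the Poisson rate ratio.
- **That every other secondary outcome is baseline-adjusted.** The wording on change covers the continuous outcomes only.

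The recommendation survives these points. Surveillance that covers these events is scheduled at baseline in both arms, and adjustment cost almost nothing in the scenarios examined. Open wording is itself a reason to fix the covariate in advance.

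**Conclusion.** The point holds as a precision improvement to one secondary outcome. It is not an error, and it does not touch the primary analysis or any stated power claim. The plan does not name prior ED or hospital use in the two Poisson models, although event surveillance covering those events is scheduled at baseline.

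The size is open. In the main simulation the gain was about nil when the log-rate correlation was 0.5 (SE ratio 0.95 to 1.01); the second model suggested slightly more. With perfectly stable rates the SE ratio was 0.97 to 1.01 at SD 0.5, 0.66 to 0.91 at SD 1.0 and 0.42 to 0.71 at SD 1.5. The largest cost seen was about 1% in SE. All of this rests on the assumed rates, heterogeneity and stability, and on a usable 6-month baseline count, which the documents imply but do not confirm.

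**What to change.** Before unblinded analysis:

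1. State the look-back period of the baseline event-surveillance form for ED visits and for hospitalizations.
2. Name each participant's baseline count over that period, for example as log(count + 0.5), as a covariate in the corresponding mixed Poisson model. A pre-randomization period with a common rate across arms would also serve. Keep the three outcome windows as they are.
3. If the form holds no usable count, pre-specify an indicator of prior use from what was recorded, such as a psychiatric hospitalization within six months of enrollment.

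If the counts were captured, the cost is a few sentences of SAP text and one more term in each model. If they were not, wording cannot create them and the indicator is the fallback. The remaining downside is reliance on self-reported recall at baseline; error in that recall would mainly reduce the gain in precision.
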